## Statistical analysis plan for KetMo, NCT 05422001

Aarhus. September 15th 2023

The following plan for data analysis was decided upon at a meeting with all members of the steering committee on September 15th, 2023. The plan was made before A and B lists were obtained from the hospital pharmacy.

This study will be undertaken as an equivalence trial with the application of intention to treat analysis.

Missing data are assumed to be missing at random, no imputations.

In brief:

A study enrollment flow diagram in accordance with the CONSORT (Consolidated Standards of Reporting Trials) will be prepared. Patient characteristics and outcome measures will be reported as means, standard deviations (SDs), medians, interquartile ranges (IQRs), and percentages, as appropriate.

Primary outcome will be comparing average change of NRS at 10 minutes between the intervention and control group and analyzed using appropriate test depending on distribution. Primary outcome includes initial analysis of all included patients (n=116) and sub-analysis in two groups (prior opioid use / no prior opioid use). Appropriate test according to potential difference in NRS at T0 in the two groups (prior opioid use) will be applied for comparing the differences in NRS between the two groups.

NRS will be reported as median (interquartile range) and compared between groups at the various times using the Mann–Whitney U test. If normal distributed a multilevel mixed effects linear regression will be carried out.

Categorical data (number of patients with Ramsay Sedation Scale Level 2, any adverse events during observation) are reported as numbers (%) with 95% confidence intervals and compared using the  $\chi^2$  test. Analysis of other secondary outcomes will be dichotomized and presented for relevant time points,  $\chi^2$  test.

Secondary outcome concerning Rescue opioid will be evaluated as time to event (opioid) – non parametric – Kaplan Meier estimate will be considered, if appropriate. Alternative rescue opioid yes/no – binary regression if assumptions are fulfilled.

All P-values will be two-sided, and those below 0.05 considered significant.

Detailed statistical plan are written, printed, signed and stored in Trial Master File

[name]

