## 2.5 TRIAL PROCEDURES

## 2.5.1 Patients

The trial procedures will be limited to the interventions given with the first dose of morphine (see section 2.3)

Data will be obtained from the study specific eCRF and from the electronic medical records.

 $T_0$  defined as when the ED physician/nurse evaluates NRS and the PI gives the study medication.

The trial and observation period is  $T_0$  - 120 min.

	T 0	10 min	20 min	30 min	45 min	60 min	120 min
NRS	Х	х	Х	Х	Х	Х	х

Patient rated		Х					Х
pain relief*							
Vital	Χ	Х	Х	Χ	Х	Χ	Х
parameters							
Patient		х		Х			х
reported side							
effects**							
Physician							х
reported side							
effects***							
Provider							x
satisfaction							
score****							
Patient							x
satisfaction							
score							
RASS****	 	Х	Х	Х	Х	Х	Х

\*Patients will be asked to rate their pain relief on a 6-point scale ("worse pain," "no," "little," "moderate," "good," or "complete pain relief").

In addition, patients are encouraged to spontaneously report any other side effects/adverse advent. The timing of onset and resolution of all adverse effects during the observation period will be recorded.

- \*\*\*Physician-reported side effects: nystagmus, hypertension, respiratory depression, bradycardia, hallucinations.
- \*\*\*\*Provider satisfaction with pain control will be recorded on the 4-point Likert scale with 0 being "completely unsatisfied" and 3 being "very satisfied.
- \*\*\*\*\*Richmond Agitation-Sedation Scale (RASS) will be used to evaluate agitation or sedation. (appendix 2)

TRIAGE and TOKS (tidlig opsporing af kritisk sygdom) according to the standard at AUH will be used to evaluate differences in vital parameters.

\*\*Patient-Reported Side effects: nausea, lightheadedness or dizziness, disorientation, euphoria, itching, tinnitus, double vision, abnormal dreaming or hallucinations.

There will be no questionnaires for the participants to answer, they will be asked verbally and their answers will be entered in RedCap.

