# Appendix 2, Richmond Agitation and Sedation Scale

		Richmond Agitation and Sedation Scale			
( Rass)					
+4	Combative	Violent, immediate danger to staff			
+3	Very Agitated	Pulls or removes tube (s) or catheters; aggressive			
+2	Agitated	Frequent non-purposeful movement, fights ventilator			
+1	Restless	Anxious, apprehensive but movements not aggressive or vigorous			
0	Alert and Calm				
-1	Drowsy	Not fully alert, but has sustained awakening to voice (eye opening			
		and contact > 10 sec)			
-2	Light sedation	Briefly awakens to voice (eye opening & contact < 10 sec)			
-3	Moderate sedation	Movement or eye opening to voice (but no eye contact)			
-4	Deep sedation	No response to voice, but movement or eye opening to physical			
		stimulation			
-5	Unarousable	No response to voice or physical stimulation			

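### The public SAP counts a Ramsay sedation level, but the protocol collects RASS; name RASS and state signed cut-offs

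*SAP*

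**What the plan says.** The SAP's paragraph on categorical data names two items: the "number of patients with Ramsay Sedation Scale Level 2" and any adverse event during observation. Both are to be given as numbers and percentages with 95% confidence intervals and compared by chi-square. For everything else it adds a general rule: "Analysis of other secondary outcomes will be dichotomized and presented for relevant time points". It also has a general reporting sentence: "Patient characteristics and outcome measures will be reported as means, standard deviations (SDs), medians, interquartile ranges (IQRs), and percentages, as appropriate".

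Protocol section 2.5.1 names a different instrument: "Richmond Agitation-Sedation Scale (RASS) will be used to evaluate agitation or sedation". Its schedule marks RASS at 10, 20, 30, 45, 60 and 120 minutes and not at T0. Section 6.2.2 lists RASS among the variables recorded at those times. Appendix 2 prints the scale from +4 to -5. The visible protocol does not mention Ramsay, and the amendment list records no change of sedation scale.

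**The concern.** The SAP specifies a count on one scale, and the protocol schedules data on another. If RASS was meant, the level still lacks a sign, and the sign decides whether the row counts sedated or agitated patients. Someone would have to settle the scale, level and direction after data collection, which is what a plan fixed before the allocation lists arrive is meant to avoid.

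The stake is modest. Protocol section 2.1.2 expects side effects to be similarly frequent in the two arms, and this is one of only two items the SAP's categorical paragraph names. Linking RASS to that hypothesis is an inference, because neither sedation nor agitation is in the protocol's lists of patient- or physician-reported side effects.

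**Working it through.** The plan states no figure on this point, so the check sets the texts side by side.

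1. **Scale.** SAP: Ramsay. Protocol sections 2.5.1 and 6.2.2 and Appendix 2: RASS only. Neither document converts one scale to the other. Protocol version 3.2 is dated 26 May 2023 and the SAP 15 September 2023. The SAP does not announce a new instrument.

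2. **Level.** In Appendix 2, RASS has 4 levels above zero, 1 calm level at zero and 5 levels below: 4 + 1 + 5 = 10. The number 2 occurs twice:
   - +2, Agitated: "Frequent non-purposeful movement, fights ventilator"
   - -2, Light sedation: "Briefly awakens to voice (eye opening & contact < 10 sec"

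   These lie on opposite sides of calm, so replacing the word Ramsay with RASS does not define the count.

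3. **Do the SAP's other sentences supply the rule?** The rule for other secondary outcomes says to dichotomize but gives no scale and no cut-off. The general reporting sentence gives neither. The generic Fisher's exact test in protocol section 5.1 also needs categories to be defined first.

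4. **One direction or two?** Section 2.5.1 uses RASS for both agitation and sedation. A single sedation cut-off would place agitated patients with calm ones, and a single agitation cut-off would place sedated patients with calm ones. One row per direction avoids this.

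5. **Mild readings.** There is no T0 RASS, so change from baseline cannot be derived. Level +1 is "Anxious, apprehensive but movements not aggressive or vigorous", which may describe a patient who enters with NRS of 5 or more and is still in pain. Level -1 is "Not fully alert, but has sustained awakening to voice", which morphine may produce in either arm, since section 2.4 has it titrated until NRS is 3 or below. This favours ±2 for the main rows.

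6. **Why descriptive.** The SAP gives 116 patients. No split by arm is stated, so 116/2 = 58 per arm is an assumption. Exact (Clopper-Pearson) 95% intervals for one arm, at illustrative counts x out of 58, are:
   - 0/58 = 0%: 0 to 6.2%, the upper limit being 1 - 0.025^(1/58) = 0.062
   - 3/58 = 5.2%: 1.1 to 14.4%
   - 6/58 = 10.3%: 3.9 to 21.2%

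   With equal arms, the expected count per arm is half the total number of events, so chi-square needs at least 2 × 5 = 10 events in total for every expected count to reach 5. Protocol section 1.2.4 anticipates few psychoperceptual effects at 0.1 mg/kg. These figures show how the replacement rows should be read; they do not measure the defect.

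**The case against.** Four objections deserve an answer.

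- **The count may be possible after all.** Protocol section 6.2.1 calls its variable list an overview and leaves the detail to a data dictionary. The SAP describes itself as brief and points to a detailed plan in the Trial Master File. Neither is visible, and either could hold a Ramsay field or a mapping. This stands. A reader might infer that the analysis is impossible, but the documents support only that it cannot be produced from the data the protocol lists.

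- **The intended sign is fairly clear.** The SAP's item is a count on a sedation scale, so if RASS was meant, -2 is the natural reading and +2 is strained. This stands as a statement of likelihood, so the two readings should not be given equal weight. The sign is still not written down, and a row at -2 alone would leave agitation uncounted.

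- **RASS may already have an analysis route.** Section 4.2.1 lists side effects as a secondary outcome, and section 4.3.1 says harm will be captured in the secondary outcomes. The SAP's dichotomizing rule can therefore plausibly cover RASS. A reader might infer that RASS is left with no planned analysis, and the documents do not show that. What is missing is the scale's name and a cut-off. Agitation may also surface through side effects that patients report spontaneously.

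- **A long set of new rows would be preference.** This stands. The documents do not dictate particular thresholds. The correction needs only the right scale, signed cut-offs and one row per direction.

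**Conclusion.** The SAP's sedation item is wrong as written. It names a scale that the visible protocol does not collect, and a bare level 2 is undefined on the scale that it does collect. The impact is low: one secondary safety table. The primary outcome, the sample size and the significance level are unaffected. A reader might go further and conclude that the trial's safety comparison is compromised. The documents do not support that, since adverse events and side effects are recorded and reported separately.

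Confidence in the mismatch is high, because it rests on the wording alone. That the count cannot be made rests on the assumption that no Ramsay field or mapping exists in the data dictionary or the Trial Master File plan.

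**What to change.** Replace the Ramsay item with RASS and state signed cut-offs before the A and B lists are used. Suggested wording: RASS, descriptive; by arm, n (%) with 95% confidence interval for patients with any reading of -2 or lower (sedation) and, separately, any reading of +2 or higher (agitation) from 10 to 120 minutes, among patients with at least one RASS reading; a patient with both is counted in both rows.

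Rows at -1 or lower and +1 or higher, or the full RASS distribution by arm and time point, are optional. Add a note that there is no T0 reading, so +1 may reflect pain and -1 may reflect morphine. If a Ramsay field or a mapping does exist, stating it in the public SAP would be enough.

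The cost is one SAP phrase and two table rows from data already scheduled. The SAP predates receipt of the allocation lists, so a correction made before those lists are used needs no unblinding. If they have already been used, the change should be dated and described as made afterwards. The drawback is that counts may be small and intervals wide.

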#### 2.2 ALLOCATION

Patients fulfilling all inclusion criteria and no exclusion criteria will be randomized as follows:

Group 1 = patients with a prior use of opioids.

Group 2 = patients without a prior use of opioids.

Patients in group 1 are allocated randomization numbers 101-190

Patients in group 2 are allocated randomization numbers 201-290

There are 10 additional numbers in each group to be used if a patient is excluded after the administration of study medicine.

If a patient is excluded after randomization, but before study medicine is administered, the randomization number can be re-used by adding and registering a, b, c and so on.

Patients (n=160) will be randomized in a 1:1 ratio to either s-ketamine or placebo (NaCl) in blocks of 2, 4 and 6 patients

The randomization process will be performed by the hospital pharmacy using www.sealedenvelope.com.

The randomization list is kept at the hospital pharmacy during the study and only delivered to the PI when the inclusion and the data analysis are completed.

PI will be provided with numbered blinded kits including either S-ketamine or placebo ensuring allocation concealment.

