#### 5. SAMPLE SIZE CALCULATION AND STATISTICAL ANALYSIS PLAN

## 5.1 Sample size calculation

We consider a mean reduction in pain intensity of 1 (SD  $\pm$ 2) on the NRS scale to be realistic in the control group and that the reduction should be 2.5 (SD  $\pm$  2) in the intervention group for the addition of LDK to be meaningful. Based on these estimates, an alpha of 5%, a power of 90% and a two-sample t-test (assuming that the pain reduction is normally distributed), a sample size of 78 patients is required; 39 in each treatment arm (two independent samples =156 patients).

The primary (continuous) and secondary outcomes (binary and continuous variables) will be presented as follows: Categorical variables will be compared using Fisher's exact test and continuous variables

using t-tests or Wilcoxon rank-sum test as appropriate. P < 0.05 will be considered statistically significant.

To investigate the hypothesis of heterogeneity in effect of LDK addition depending on prior morphine use, we will compare treatment effect between the two groups (no prior morphine use vs prior morphine use). If we assume the two groups to have equal size (78 patients) then the expected SE of the difference between treatment effects of the two groups (no prior morphine vs prior) will be 0.64, i.e. the corresponding 95% confidence interval will have a width of approximately 2.6.

To handle potential differences in baseline pain intensity between the standard and the LDK treatment group, we will assess the relative (%) change in NRS from baseline (T0) to 10 min after administration of study medicine in a supplemental post-hoc analysis. The relative change in pain scores will be assessed by multilevel mixed effect ordinal logistic regression model.

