**RASS** 

Need for rescue morphine and total use of morphine

Physician reported side effects: nystagmus, hypertension, respiratory depression, bradycardia, arrhythmia.

TOKS and triage values as standard procedures

Patient-reported side effects: nausea, lightheadedness or dizziness, dry mouth, disorientation, euphoria, itching, tinnitus, double vision, abnormal dreaming or hallucinations.

Patient satisfaction. To be able to compare with other and future studies "no pain" and "worst pain imaginable" are chosen as anchors.

Provider satisfaction with pain control will be recorded on the 4-point Likert scale with 0 being "completely unsatisfied" and 3 being "very satisfied.

Protocol violation.

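### The SAP dichotomises the remaining ordinal secondary outcomes, chiefly the satisfaction scores, without publishing a cut-point; a rank or proportional-odds analysis of the same data would be more powerful

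*SAP*

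**What the plan says.** The SAP gives separate methods for NRS over time (Mann–Whitney, or a mixed model), for sedation and adverse events (chi-square), and for rescue opioid (time to event, or yes/no). For the rest it says: "Analysis of other secondary outcomes will be dichotomized and presented for relevant time points", again by chi-square. It does not list the outcomes meant, the cut-points or the time points.

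The scales are described in the protocol:

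- **Provider satisfaction** (sections 2.5.1, 2.5.2 and 6.2.2): "Provider satisfaction with pain control will be recorded on the 4-point Likert scale", scored 0 to 3, at 120 minutes.
- **Patient satisfaction**: in the schedule at 120 minutes and listed in section 4.2.1. No number of points is stated. In section 6.2.2 the entry is followed by two end-points of a pain scale, which "are chosen as anchors".
- **Pain relief** (section 2.5.1): "Patients will be asked to rate their pain relief on a 6-point scale", at 10 and 120 minutes. It is not in the section 4.2.1 list.

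Protocol section 5.1 assigns Fisher's exact test to categorical variables, and says continuous variables will be compared "using t-tests or Wilcoxon rank-sum test as appropriate". It does not mention dichotomising.

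**The concern.** Provider satisfaction and pain relief are ordered scales. Reducing one to two categories treats patients on the same side of the cut as identical, which costs power with no saving in data or effort. The size of the cost depends on where the cut falls, and the public plan does not say where that is.

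At stake is the chance of detecting a difference in how patients and providers rate the treatment. The primary outcome, NRS at 10 minutes, is not affected.

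**Working it through.** **The plan's own figure.** The documents give no power figure for these scales. The only calculation is for NRS: a difference of 1.5, SD 2, 90% power and 39 per arm in each opioid group. It reproduces (38.3 by t-test, rounded up to 39; power 90.5%), but nothing below depends on it.

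**Inputs from the documents.** The SAP gives n = 116 and the protocol allocates 1:1, so 116/2 = 58 per arm, assuming an even split. Alpha is two-sided 0.05. The scales have 4 and 6 levels.

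**Assumptions.** The documents give no category distributions and no effect size for these scales. Several distributions are therefore used, and the odds ratio in step 2 is assumed to be 2.5.

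**Step 1: information kept.** Under proportional odds the information is proportional to 1 − Σp³, where p are the category shares (Whitehead). A cut with share q below it has 1 − q³ − (1−q)³ = 3q(1−q). The fraction kept is the ratio of the two.

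- Four equal categories: full scale 1 − 4×0.25³ = 0.9375. Middle cut 3×0.25 = 0.75, so 0.75/0.9375 = 80% is kept. A 25/75 cut gives 0.5625/0.9375 = 60%.
- Six equal categories: full scale 1 − 6×(1/6)³ = 0.9722. Middle cut 0.75/0.9722 = 77%. A 17/83 cut gives 0.4167/0.9722 = 43%.

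| Assumed shares (%) | Kept, best cut | Kept, worst cut |
|---|---|---|
| 25/25/25/25 | 80% | 60% |
| 5/10/35/50 | 90% | 17% |
| 10/40/40/10 | 86% | 31% |
| six equal | 77% | 43% |
| 5/15/30/30/15/5 | 80% | 15% |
| 3/12/20/30/25/10 | 72% | 9% |

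The best cut loses 10–28% and the worst 40–91%. In these cases the loss exceeds half only when about 17% or less of patients fall on one side; a 20/80 cut loses 49%.

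**Step 2: power, 58 per arm, odds ratio 2.5.** As an example, take the top category of a four-level scale, with 25% in the control arm. The odds are 0.25/0.75 = 0.333; times 2.5 gives 0.833, so 45.5% in the treated arm. The difference is 0.205 and the pooled share 0.352. The standard error is √(2×0.352×0.648/58) = 0.0887, so z = 0.205/0.0887 = 2.31. Power is about Φ(2.31 − 1.96) = 64%.

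All cuts, by exact binomial calculation, with the rank test by simulation:

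| Control shares (%), worst to best | Rank test | Chi-square at each cut, lowest to highest |
|---|---|---|
| 5/15/25/25/20/10 | 78% | 11, 39, 64, 66, 42% |
| 10/25/40/25 | 76% | 22, 57, 64% |

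The best cut costs about 12 percentage points (78 − 66 and 76 − 64). The worst costs 67 and 54.

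**The case against.** Several stronger readings are tempting, and the documents do not support them.

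- **Most of the information is thrown away.** A reader might infer this from the 11% and 22% figures. Those arise from splitting off a lowest category assumed to hold only 5% or 10% of control patients. A cut near the middle keeps about three quarters or more in most of the cases above.
- **The cut is free to be chosen on the results.** If it were picked from group results, type I error would rise to about 13–14% with three possible cuts and 18–20% with five. These are upper bounds. The published SAP calls itself brief, says a signed and more detailed plan is on file, and predates receipt of the treatment-group lists. That plan may fix the cut. The supportable statement is that the public documents do not. Protocol section 6.5 has the data analysed as groups A and B before unblinding, so the cut needs to be settled before that step, not merely before unblinding.
- **All secondary outcomes are affected.** NRS, rescue opioid, sedation and adverse events have their own methods. Only provider satisfaction is documented as a 4-point scale, and it is unclear whether the SAP sentence reaches pain relief.
- **The time points are wide open.** The schedule takes satisfaction once, at 120 minutes. Only pain relief offers a choice, between 10 and 120 minutes.
- **The protocol had promised a rank test.** Its Wilcoxon option is for continuous variables. Section 5.1 does not say how ordered scales are handled.
- **Patient satisfaction will in fact record pain.** The anchors read most naturally as a misplaced NRS sentence, and neither section 2.5.1 nor section 4.2.1 defines satisfaction by pain.

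The SAP also allows outcomes to be described by medians, interquartile ranges and percentages, so fuller description is not excluded. What stands is that the stated test is a chi-square on a dichotomy, and it has less power than a rank test at every cut examined.

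**Conclusion.** The point holds in limited form. The SAP specifies a less efficient method for the satisfaction scores, and possibly for pain relief, and the public documents give no cut. The loss is about 10–28% of the information at the best cut, and more than half only at a lopsided one. Power falls from 76–78% to 64–66% at the best cut and 11–22% at the worst. These power figures rest on the assumed distributions, an odds ratio of 2.5 and 58 per arm; for patient satisfaction, whose number of levels is not stated, they are only indicative. If the detailed plan fixes the cut, the uncertainty about its position goes, but a loss of power remains. Severity is low: secondary outcomes only, and the documents claim power only for NRS.

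**What to change.** In the SAP, replace dichotomisation as the main analysis of these scales with one pre-chosen method: a Wilcoxon test stratified by prior-opioid group, or a proportional-odds model with treatment and opioid group, reporting the odds ratio with its 95% confidence interval. Show category counts by arm. Keep any dichotomy as supportive, with its cut and time points published and fixed before any group-level result, including A versus B, is seen. State whether pain relief is a secondary outcome.

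As a wording correction in protocol section 6.2.2, state the patient satisfaction scale actually used and move the pain anchors to the NRS definition.

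The cost is a change of wording; the data are the same and no patients are added. If group-level results have already been seen, report the ordinal analysis beside the planned one and label it post hoc.

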## 2.1.2 Hypotheses

- The combination of IV LDK and IV morphine will be superior to IV morphine alone as regards analgesic effect measured as reduction on the NRS scale.
- The combination of IV LDK and IV morphine will provide a larger reduction on the NRS scale for patients with a prior use of opioids than for patients with no prior use of opioids.
- The combination of IV LDK and IV morphine will reduce the opioid consumption within the first hour.
- The frequency of side effects will be similar in the two treatment groups (ketamine vs. placebo)

\*\* After longer use (> 3 days).

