## 4.2 Secondary outcomes

## 4.2.1 Definitions

Secondary outcomes:

- Need of morphine within the 30, 60 and 120 min after administration of study medication
- Pain intensity after 20, 30, 45, 60 and 120 min
- Side effects
- Patients satisfaction Score
- Provider Satisfaction Score

 Comparison of pain reduction in the two parallel groups (prior opioid, no prior opioid) on all time intervals.

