## 4.3 Safety and harm

#### 4.3.1 General consideration

The personal in the ED are highly trained in acute pain therapy. The PI is Specialty trainee in anesthesiology, Department of Anesthesiology AUH and she will be at trial site whenever study medicine is given. The doses used in this study are very low (0,1 mg/kg), and we do not expect any serious adverse reactions with this dose. We therefore believe it is safe for both individual patients and at the group level to be enrolled into this study after relevant inclusion and exclusion criteria.

The overall benefit and potential harm will be captured in our secondary outcomes, and the clinical team/PI will document any specific adverse reactions suspected to be related to the intervention - if there are AE or AR's after the observation period ( $T_0$ - $T_{120}$ ), the patients are observed as standard on AUH.

All participants are expected to receive opioids, but the amount is hypothesized to differ.

AE as natural consequences of the reason for hospitalization will not be registered in the eCRF. (i.e. blood transfusion).

Investigators should use their knowledge of the patient, the circumstances surrounding the event, and an evaluation of any potential alternative causes to determine whether or not an AE is considered to be related to the study drug, indicating "yes" or "no" accordingly. The following guidance will be taken into consideration:

- Temporal relationship of event onset to the initiation of study drug
- Course of the event, considering especially the effects of dose reduction, discontinuation of study drug, or reintroduction of study drug (where applicable)
- Known association of the event with the study drug or with similar treatments
- Known association of the event with the disease under study
- Presence of risk factors in the patient or use of concomitant medications
  known to increase the occurrence of the event
   Presence of non-treatment-related factors that are known to be associated
  with the occurrence of the event

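### Hypothesis 3 is about the amount of opioid used in the first hour, but the public SAP names no analysis of amount: rescue opioid is time to event or yes/no

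*SAP*

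**What the plan says.** The protocol treats opioid use as a quantity. Section 2.1.2 states: "The combination of IV LDK and IV morphine will reduce the opioid consumption within the first hour". Section 4.3.1 adds: "All participants are expected to receive opioids, but the amount is hypothesized to differ". The variable list in Section 6.2.2 includes "Need for rescue morphine and total use of morphine", so both aspects are recorded.

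The listed secondary outcome in Section 4.2.1 is less clear: "Need of morphine within the 30, 60 and 120 min after administration of study medication". It could mean any further morphine or how much.

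The SAP's rescue paragraph reads "Secondary outcome concerning Rescue opioid will be evaluated as time to event (opioid"), with a Kaplan-Meier estimate to be considered. It continues "Alternative rescue opioid yes/no", by binary regression. It sets no 60-minute window for this outcome. For the rest it says: "Analysis of other secondary outcomes will be dichotomized and presented for relevant time points", using a chi-square test. It closes with: "Detailed statistical plan are written, printed, signed and stored in Trial Master File".

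Protocol Section 5.1 has a general rule: secondary outcomes are binary or continuous, and continuous ones are compared by t-test or Wilcoxon rank-sum test. It does not mention opioid amount.

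**The concern.** Time to first rescue and any rescue both stop counting at the first rescue dose. Dose size and repeat doses drop out. Repeat doses are to be expected, because Section 2.4 describes titrating morphine to a pain target. Section 4.3.1 itself expects everyone to receive opioid and places the difference in amount.

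Followed as written, the public SAP would therefore not test hypothesis 3 on its own quantity. Two choices that change the answer are also open: whether the first morphine dose counts, and how the two dosing scales in Section 2.3.1 (mg/kg for non-users, a percentage of daily opioid for prior users) are handled. If these are settled after results are known, the choice of analysis can follow the data.

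**Working it through.** **1. Text comparison.** This carries the point. The documents give no figure for opioid amount to reproduce; the sample size concerns pain at 10 minutes.

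| Source | Quantity addressed | Is amount tested? |
|---|---|---|
| Protocol 2.1.2 and 4.3.1 | Amount of opioid | This is the hypothesis |
| Protocol 4.2.1 | Need at 30, 60, 120 min | Ambiguous |
| Protocol 6.2.2 | Rescue need and total morphine | Data collected |
| Protocol 5.1 | Continuous secondary outcomes in general | Possible, not linked to opioid |
| SAP, rescue paragraph | Time to event, or yes/no | No |
| SAP, other secondary outcomes | Dichotomised | No |
| SAP, descriptive sentence | Means, medians and so on | Summary only |

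If total morphine falls under the SAP's rule for other secondary outcomes, it is dichotomised. If it falls under Section 5.1, it is compared as a continuous variable. The public documents do not say which applies.

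**2. What the named analyses leave out.** Assume rescue doses in 60 minutes are Poisson with mean m, and LDK cuts m by a third. Then P(any rescue) = 1 − exp(−m), and the share of doses that are repeats = 1 − (1 − exp(−m))/m.

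| m, placebo vs LDK | Any rescue | Relative cut in yes/no | Repeat share |
|---|---|---|---|
| 0.75 vs 0.5 | 53% vs 39% | 25% | 30% vs 21% |
| 1.5 vs 1.0 | 78% vs 63% | 19% | 48% vs 37% |
| 3 vs 2 | 95% vs 86% | 9% | 68% vs 57% |

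A limiting case: let any-rescue be equal in both arms (0.4, 0.6 or 0.8) and the dose among those rescued average 10 vs 5 mg (SD 4), with 58 per arm. The yes/no chi-square test then rejects in about 4–5% of simulated trials, which is the alpha level. A t-test on amount rejects in 59%, 88% and 99%, and Mann-Whitney in 18%, 59% and 97%.

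**3. Illustrative power.** Assumed inputs:
- 58 per arm (the SAP's 116 ÷ 2), half of them prior users; two-sided 5%; 4,000 simulated trials per setting.
- Non-users: 70 kg × uniform 0.05–0.1 mg/kg per dose. Prior users: lognormal with median 1, 2 or 3 × 5.25 mg and log-SD 0.6. Repeat doses equal the patient's first.
- Rescue times uniform over 60 minutes. The SAP names no test beyond Kaplan-Meier, so log-rank is assumed; uncorrected chi-square stands in for binary regression.

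Ranges run over the three medians.

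| m | Log-rank | Yes/no | Stratified rank test, rescue mg | Same, total mg with first dose |
|---|---|---|---|---|
| 0.75 vs 0.5 | 31–33% | 30–32% | 33–35% | 20–22% |
| 1.5 vs 1.0 | 44–45% | 39–42% | 54–55% | 42–44% |
| 3 vs 2 | 55–56% | 36–37% | 79–80% | 70–71% |

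The stratified rank test is van Elteren. On rescue mg its gain over log-rank is about 2, 10 and 24 points. With overdispersed counts (gamma shape 2) the two larger gains fall to about 8 (36–37% against 29%) and 16 (47–48% against 31–32%). With equal means (1.5 or 3) the log-rank, yes/no and van Elteren tests reject in 4.6–5.3% of trials.

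**4. Where the gain does not hold.**
- Total mg: at 1.5 vs 1.0 the gain disappears, and at 0.75 vs 0.5 it reverses.
- Untransformed regression on rescue mg with robust SE: 22–29%, 37–50% and 48–70%, against 31–33%, 43–48% and 54–57% for log-rank across repeat runs. It is not reliably better.
- Unstratified rank test on total mg: 21–42% at 1.5 vs 1.0 and 45–70% at 3 vs 2, against 42–44% and 70–71% stratified.
- The model leaves out the minimum dose for prior users in the Trial flowchart footnote. Adding a floor moves total-mg power at 3 vs 2 from 71% to 79% at the 1x median.

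**The case against.** The strongest reply is that Section 5.1 already covers this. A rule by variable type need not list every variable, and total morphine is continuous. That would settle the matter if the protocol stood alone. But the SAP sets a different rule for rescue opioid and dichotomises other secondary outcomes, so a reader cannot tell which governs. Section 5.1 also names an unstratified test, although two dosing scales are mixed.

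Second, the listed outcome is need, and time to rescue or yes/no are reasonable analyses of need. This stands in part: the mismatch begins inside the protocol, between Sections 2.1.2 and 4.2.1, and both documents should be aligned.

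Third, the SAP's sentence on means, SDs, medians and IQRs could produce a dose summary by arm. It could, but it provides no test of hypothesis 3.

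Fourth, the SAP presents itself as a summary, and the detailed plan may contain the analysis. This cannot be checked. A reader might infer that no amount analysis is planned at all; the documents do not support that.

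A reader might also infer that analysing mg is more powerful whichever way it is done. Step 4 shows that it is not.

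**Conclusion.** The point holds for the public documents. Hypothesis 3 concerns amount and the data are collected, yet the SAP's named analyses do not measure amount, and its dichotomising rule conflicts with the one protocol rule that could. This rests on the text and needs no assumed rates.

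The power figures are secondary. The documents give no rescue counts or dose spread, so every input in steps 2 and 3 is an assumption. The gain belongs to the stratified rank test on rescue mg and depends on rescue being fairly frequent. The case for change is that the analysis should match the hypothesis.

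This is a secondary hypothesis. Nothing here touches the primary analysis or the sample size. It should be corrected, but it does not threaten the trial's main result.

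**What to change.** State in the SAP that the analysis variable for hypothesis 3 is cumulative opioid, in IV morphine equivalents, from T0 to 60 minutes, with 30 and 120 minutes as further windows. Align protocol Section 4.2.1 by saying that amount is meant.

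Define the variable as opioid given after the first morphine dose, with the total including that dose as a sensitivity analysis. Section 2.5.1 has the first dose accompany the study medication, so the study drug cannot yet have influenced it.

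Test with a rank test stratified by prior opioid use (van Elteren). Report either the stratified Hodges-Lehmann shift or the adjusted mean difference in mg with a 95% CI, and choose which now. Keep time to first rescue and yes/no as supportive.

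The cost is a paragraph of SAP wording, a matching line in the protocol and one extra analysis of data already collected. If the detailed plan already specifies such an analysis, move that text into the public SAP. If the A and B lists have already been obtained, label the analysis as added afterwards.
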